1.2 Research Hypothesis

BMS-986141 is effective in reducing the recurrence of stroke in subjects with recent TIA or stroke.

1.3 Objectives(s)

1.3.1 Primary Objectives

To determine the dose-response relationship of BMS-986141 on the recurrence of brain infarction at 28 days as assessed by a composite of symptomatic ischemic stroke and unrecognized brain infarction as assessed by MRI in subjects with ischemic stroke or TIA treated with ASA.

1.3.2 Secondary Objectives

- To assess the effect of BMS-986141 on the occurrence of major adverse cardiovascular events (MACE, including all stroke, myocardial infarction, and CV death) by Day 90
- To assess the effect of BMS-986141 on the occurrence of the composite of ischemic stroke, myocardial infarction, and CV death by Day 90
- To assess the effect of BMS-986141 on incidence of symptomatic recurrent ischemic stroke up to 28 days of treatment
- To assess the effect of BMS-986141 on the occurrence of the composite of unrecognized brain infarction assessed by MRI at Day 28 and MACE by Day 90

1.3.3 Safety Objectives

- To assess the effect of BMS-986141 on the composite of Major and Clinically Relevant Non-Major (CRNM) Bleeding
- To assess the effect of BMS-986141 on all reported bleeding
- To evaluate safety and tolerability of BMS-986141

1.3.4 Exploratory objectives

- [REDACTED]

1.4 Product Development Background

The Investigator Brochure (IB) for BMS-986141 provides detailed information on the preclinical pharmacology, toxicology, metabolism, pharmacokinetics, and potential for drug-drug interactions of BMS-986141. The clinical experience to date is summarized below, and additional detail can be found in the IB.

1.4.1 Clinical Pharmacology and Safety

Preliminary data have been reviewed on a total of 116 subjects who have received single doses of BMS-986141 of up to 150 mg and multiple doses of up to 30 mg QD for up to 14 days in study CV006003. This includes subjects receiving multiple doses of 20 mg QD or placebo co-administered with ASA 325 mg QD for up to 14 days and subjects who received single doses of BMS-986141 in the presence of itraconazole, a strong cytochrome P450 (CYP) 3A4 inhibitor. Preliminary results show dose proportional PK and a consistent concentration-dependent PD effect. In addition, exposures in subjects who also received itraconazole increased up to 8-fold and the half-life of BMS-986141 increased ~3-fold.

Review of preliminary safety data showed no clinically significant AEs or laboratory abnormalities, including coagulation profiles, template bleeding times, BUN, creatinine, bilirubin, or hepatic enzymes. This includes all subjects who received BMS-986141 co-administered with ASA and BMS-986141 co-administered with itraconazole.

1.4.1.1 Pharmacokinetics of BMS-986141

BMS-986141 was rapidly absorbed following oral administration to fasted healthy subjects, with maximum concentrations achieved between 1.75-3 hours. The mean terminal half-life of BMS-986141 was between 35.2-45.5 hours. The accumulation index was < 2 (ranging from 1.3 to 1.9). Both maximum concentration (C_{max}) and total drug exposures of BMS-986141 increased in a dose-proportional manner.

There are 3 major circulating metabolites of BMS-986141; BMT-162856 (700 – fold less active), BMT-181551, and BMT-162853. Exposures of BMT-162856 were 6.8-36.4-fold higher than BMS-986141, with the exposures of the other metabolites much lower than BMS-986141. The exposures of BMS-986141 and its major circulating metabolites are expected to be below no-observed-adverse-effect level (NOAEL) exposures at all doses. All metabolites are expected to have minimal contribution to the overall PD effect.

1.4.1.2 Dose Selection

A combination of preclinical efficacy and safety data, inhibition of human ex vivo platelet aggregation, and Phase 1 PK, PD and safety have been taken into consideration in selecting doses for this study. Doses have been selected to optimize the ability to address the primary objective, which is to determine the dose-response relationship of BMS-986141 on the recurrence of brain infarction at 28 days as assessed by a composite of symptomatic ischemic stroke by Day 28 and unrecognized brain infarction as assessed by MRI.

1.5 Overall Risk/Benefit Assessment

The current study is a Phase 2 study of BMS-986141 in patients with ischemic stroke or TIA who are also receiving ASA. Prior to this study BMS-986141 has only been dosed in healthy subjects.

Preclinical studies in non-human primates suggest that BMS 986141 may be more effective at preventing the growth of an arterial thrombus than treatment with ASA alone. Furthermore, substantial antithrombotic efficacy has been observed at doses which increase provoked bleeding to an extent that is comparable to or less than that of ASA. Thus BMS-986141 may have the potential to provide an improved benefit-risk profile compared to existing therapies for the prevention and/or treatment of atherothrombotic diseases such as stroke.

The study and dosing scheme described herein has been designed to minimize risks to study subjects and is based on the previous clinical experience in healthy subjects and preclinical toxicity studies as described in the Investigator Brochure. There were no adverse findings in 28-day preclinical toxicology studies. In 3-month studies, the major preclinical findings of note were microscopic changes in kidneys of some of the monkeys that received the highest dose of BMS-986141, 75 mg/kg/day. These changes have been characterized as moderate degeneration and regeneration of tubular epithelium, and the effect was not observed one month after cessation of dosing. Monitoring of kidney function, urinalysis, and exploratory renal biomarkers will occur throughout the treatment period to facilitate early identification of renal abnormalities in subjects in the study.

The doses selected for this study are projected to span the anticipated pharmacologically active dose range and are considered within the safety margin indicated by the preclinical toxicology and the clinical experience in healthy volunteers. Of note, co-administration of moderate inhibitors of CYP3A4 (eg, diltiazem, verapamil) have the potential of increasing exposures of BMS-986141 beyond those observed with ASA co-administration. However, it is not anticipated that exposures will exceed those observed in Phase 1 study (CV006003).

While bleeding was not observed to any significant degree either pre-clinically or in healthy volunteers, there is a potential risk of bleeding with any antithrombotic agent. There will therefore be close monitoring of subjects for bleeding and oversight of the study by an independent Data Monitoring Committee (DMC).

2 ETHICAL CONSIDERATIONS

2.1 Good Clinical Practice

This study will be conducted in accordance with Good Clinical Practice (GCP), as defined by the International Conference on Harmonisation (ICH) and in accordance with the ethical principles underlying European Union Directive 2001/20/EC and the United States Code of Federal Regulations, Title 21, Part 50 (21CFR50).

The study will be conducted in compliance with the protocol. The protocol and any amendments and the subject informed consent will receive Institutional Review Board/Independent Ethics Committee (IRB/IEC) approval/favorable opinion prior to initiation of the study.

All potential serious breaches must be reported to BMS immediately. A serious breach is a breach of the conditions and principles of GCP in connection with the study or the protocol, which is likely to affect, to a significant degree, the safety or physical or mental integrity of the subjects of the study or the scientific value of the study.

Personnel involved in conducting this study will be qualified by education, training, and experience to perform their respective tasks.

This study will not use the services of study personnel where sanctions have been invoked or where there has been scientific misconduct or fraud (eg, loss of medical licensure, debarment).

2.2 Institutional Review Board/Independent Ethics Committee

Before study initiation, the investigator must have written and dated approval/favorable opinion from the IRB/IEC for the protocol, consent form, subject recruitment materials (eg, advertisements), and any other written information to be provided to subjects. The investigator or BMS should also provide the IRB/IEC with a copy of the Investigator Brochure or product labeling information to be provided to subjects and any updates.

The investigator or BMS should provide the IRB/IEC with reports, updates and other information (eg, expedited safety reports, amendments, and administrative letters) according to regulatory requirements or institution procedures.

2.3 Informed Consent

Investigators must ensure that subjects are clearly and fully informed about the purpose, potential risks, and other critical issues regarding clinical studies in which they volunteer to participate.

In situations where consent cannot be given to subjects, their legally acceptable representatives (as per country guidelines) are clearly and fully informed about the purpose, potential risks, and other critical issues regarding clinical studies in which the subject volunteers to participate.

BMS will provide the investigator with an appropriate (ie, Global or Local) sample informed consent form which will include all elements required by ICH, GCP and applicable regulatory requirements. The sample informed consent form will adhere to the ethical principles that have their origin in the Declaration of Helsinki.

Investigators must:

- Provide a copy of the consent form and written information about the study in the language in which the subject is most proficient prior to clinical study participation. The language must be non-technical and easily understood
- Allow time necessary for subject or subject's legally acceptable representative to inquire about the details of the study
- Obtain an informed consent signed and personally dated by the subject or the subject's legally acceptable representative and by the person who conducted the informed consent discussion
- Obtain the IRB/IEC's written approval/favorable opinion of the written informed consent form and any other information to be provided to the subjects, prior to the beginning of the study, and after any revisions are completed for new information.

If informed consent is initially given by a subject's legally acceptable representative or legal guardian, and the subject subsequently becomes capable of making and communicating his or her informed consent during the study, consent must additionally be obtained from the subject.

Revise the informed consent whenever important new information becomes available that is relevant to the subject's consent. The investigator, or a person designated by the investigator, should fully inform the subject or the subject's legally acceptable representative or legal guardian, of all pertinent aspects of the study and of any new information relevant to the subject's willingness to continue participation in the study. This communication should be documented.

The confidentiality of records that could identify subjects must be protected, respecting the privacy and confidentiality rules applicable to regulatory requirements, the subjects' signed ICF and, in the United States, the subjects' signed HIPAA Authorization.

The consent form must also include a statement that BMS and regulatory authorities have direct access to subject records.

Subjects unable to give their written consent (eg, stroke or subjects with severe dementia) may only be enrolled in the study with the consent of a legally acceptable representative. The subject must also be informed about the nature of the study to the extent compatible with his or her understanding, and should this subject become capable, he or she should personally sign and date the consent form as soon as possible. The explicit wish of a subject who is unable to give his or her written consent, but who is capable of forming an opinion and assessing information to refuse participation in, or to be withdrawn from, the clinical study at any time should be considered by the investigator.

The rights, safety, and well-being of the study subjects are the most important considerations and should prevail over interests of science and society.

3 INVESTIGATIONAL PLAN

3.1 Study Design and Duration

This is a randomized, double-blind, placebo-controlled, parallel-arm, study to evaluate the efficacy and safety of BMS-986141 in addition to ASA in subjects following acute ischemic stroke or TIA. Eligible subjects will be screened for possible inclusion in the study as soon as possible after arrival at the hospital, and randomized within 48 hours of the time they were last seen normal prior to acute ischemic stroke/TIA. In order to study subjects during their period of highest risk for recurrent stroke, randomization and treatment as early as possible after admission to the hospital is preferred. A baseline study-specific MRI evaluation must be performed no later than 24 hours after randomization.

The study will be conducted in two parts. Subjects in both parts of the study will be randomly assigned to one of three different doses of BMS-986141 or matching placebo, and will continue on the assigned dose for the duration of the treatment period. Approximately 1312 subjects will be randomized into the study in total. Initially randomization will be limited to the two lower doses of BMS-986141 or placebo. Randomization to the highest dose of BMS-986141 will only be initiated after DMC review of safety and laboratory data from the Day 28 study visit for at least 10% of the planned total subjects.

[figure not shown]
In Part 1 of the study, the treatment period will be 28 days. Part 2 of the study will only be initiated after regulatory review of reports from 90-day nonclinical toxicology studies that were recently completed. The treatment period in Part 2 will be 90 days. Subjects that are entered into Part 1 of the study will not be allowed to enter into Part 2.

The primary efficacy endpoint will be assessed at 28 days after the initial dose in all subjects. Additional objectives will be assessed at 28 or 90 days.

[figure not shown]
The study design schematic is presented in [Figure 3.1-1](#).

Figure 3.1-1: Study Design Schematic

CV006-004 Study Schematic - Part 1 of study

CV006-004 Study Schematic - Part 2 of study

Screening Period

Subjects with acute ischemic stroke or TIA will be evaluated for study eligibility. Subjects should be evaluated and treated according to the local standard of care. Subjects who meet the inclusion/exclusion criteria are eligible. In order to prevent overrepresentation of lacunar infarction in the study population, subjects with lacunar infarction will not be able to be

randomized after a limit of approximately 20% of the total study population have been randomized with lacunar infarction. This limit will be imposed by the study IVRS. Informed consent must be obtained before any study-specific procedures are performed. Local laboratory values will be used for assessment of eligibility. A head MRI that meets criteria established for the study will be required in all subjects within 24 hours of randomization. It is preferred that imaging be performed as early as possible after enrollment. Imaging may be performed before randomization but should not be a cause of delayed randomization. Images obtained prior to screening will only be acceptable if performed under the same criteria that will be established for the Day 28 MRI. Similarly, any other study related procedures including but not limited to physical examination (PE), vital signs, or laboratory work performed as part of standard of care may be used as screening data if they meet the requirements of the study protocol.

Randomization (Day 1)

Subjects must be randomized within 48 hours of onset of symptoms of stroke or TIA. If symptoms are present on awakening, the time for onset of symptoms should be considered as the time at which they were last seen normal. Subjects will be randomized via IVRS to one of three doses of BMS-986141 or placebo. All subjects will receive open-label ASA at a dose from 75 to 162 mg per day beginning at a time consistent with local standard of care for patients with acute ischemic stroke or TIA.

Treatment Period

Subjects should receive the first dose of study medication as soon as possible after randomization and continue with once daily dosing for the duration of the treatment period. Dosing after Day 1 should be in the morning, and must be done while fasting. Subjects who receive their first dose of study medication in the afternoon or evening should be given their second dose on the morning of the second day. Subjects should be made aware of the signs or symptoms of recurrent stroke, and instructed to report any adverse events.

A study visit will be performed on the day of hospital discharge. Subjects will be instructed to report any adverse events occurring after hospital discharge, including any occurrence of bleeding or signs or symptoms of recurrent stroke.

The study site will contact the subject by telephone on Day 10 \pm 3 days to assess study medication compliance and assess the subject's health status.

A study visit will be performed 28 \pm 3 days after the first dose of study medication. Head MRI will be performed for assessment of unrecognized brain infarctions. For subjects enrolled in Part 1 of the study, Day 28 will be the end of the treatment period and it is preferred that the study visit be performed on Day 28 or earlier.

Part 2 of the study will only be initiated after regulatory review of 90-day preclinical toxicology study reports and the updated Investigator Brochure. For subjects enrolled in Part 2 of the study, the treatment period will be 90 days. There will be no change in study visits through Day 28. Additional treatment period study visits for these subjects will occur 56 and 90 days after the beginning of the treatment period.

Pharmacokinetic (PK) sampling will be performed in all subjects. See [Section 5.5](#).

A sub-study conducted at select sites will enroll approximately 50 subjects per arm for which additional blood will be collected for analysis of platelet aggregation as a pharmacodynamic biomarker. See [Section 5.6](#).

Follow-Up Period

The follow-up period will last until the later of 90 days after the first dose of study drug or 30 days after treatment discontinuation. Subjects will be instructed to report any adverse events that occur during the follow-up period. No additional study assessments are planned at the follow-up visit, which may be an in-person study visit or if necessary conducted by telephone.

Duration of Study

The expected duration of the study, from first subject, first visit through the last subject, last follow-up visit (eg, the End of the study), is approximately 28 months.

3.2 Post Study Access to Therapy

At the end of the study treatment period, BMS will not continue to provide BMS supplied study drug to subjects/investigators unless BMS chooses to extend the study. The investigator should ensure that the subject receives appropriate standard of care to treat the condition under study.

Treatment codes will be provided to the investigators following the final database lock and after unblinding by BMS.

3.3 Study Population

For entry into the study, the following criteria MUST be met.

3.3.1 Inclusion Criteria

1. Signed Written Informed Consent

- a) Subjects or Legally Acceptable Representatives (LAR), must be willing and able to give signed and dated written informed consent. (Note: Consent by a LAR will only be allowed if permitted by local regulations.)

2. Target Population

- a) Either acute ischemic stroke or high-risk TIA as defined here
 - i) Acute ischemic stroke, defined as:
 - (1) Neurological deficit attributed to the focal brain ischemia, and either of the following:
 - Persistent signs or symptoms of the ischemic event at the time of randomization
 - Acute, ischemic brain lesion documented by computed tomography (CT) scan or MRI

AND

(2) National Institutes of Health Stroke Score (NIHSS) ≤ 7

ii) High-risk TIA, defined as:

(1) Neurological deficit of acute onset attributed to focal ischemia of the brain by history or examination with complete resolution of the deficit, and at least one of the following:

- ABCD2 score ≥ 4 OR motor or speech symptoms
- Symptomatic intracranial arterial occlusive disease documented by transcranial Doppler, ultrasound or vascular imaging, defined as at least 50% narrowing in diameter of a vessel that could account for the clinical presentation
- Documented internal carotid arterial occlusive disease, defined as at least 50% narrowing in diameter of a vessel that is presumed to be atherosclerotic and could account for the clinical presentation
- Documented stenosis in the vertebral circulation that is presumed to be atherosclerotic and could account for the clinical presentation

- b) CT or MRI ruling out hemorrhage or other pathology, such as vascular malformation, tumor, or abscess that could explain symptoms or contraindicate therapy
- c) Randomization occurring within 48 hours after onset of symptoms; if the time of onset of symptoms is unknown, such as when symptoms are first present on awakening, onset should be considered as time last seen normal
- d) Subject is able to be evaluated by study-specific MRI no later than 24 hours after randomization, does not have contraindications to the performance of the MRI, and has suitable weight and circumference. See [Section 3.4.3](#) for further details.
- e) Ability to tolerate ASA at a dose from 75 to 162 mg/day
- f) Subject Re-enrollment: This study does not permit the re-enrollment of a subject that has discontinued the study as a pre-treatment failure

3. Age and Reproductive Status

- a) Males and females, minimum age ≥ 18 years old or age of majority (if local age of majority is > 18 years of age) at the time of the screening visit
- b) Women of childbearing potential (WOCBP) must have a negative serum or urine pregnancy test (minimum sensitivity 25 IU/L or equivalent units of HCG) within 24 hours prior to the start of study drug
- c) Women must not be breastfeeding
- d) WOCBP must agree to follow instructions for method(s) of contraception for the duration of treatment with study drug (s) BMS-986141 plus 5 half-lives of study drug BMS-986141 (6 days) plus 30 days (duration of ovulatory cycle) for a total of 36 days post-treatment completion

- e) Males who are sexually active with WOCBP must agree to follow instructions for method(s) of contraception for the duration of treatment with study drug (s) BMS-986141 plus 5 half-lives of the study drug (6 days) plus 90 days (duration of sperm turnover) for a total of 96 days post-treatment completion. In addition, male subjects must be willing to refrain from sperm donation during this time.
- f) Azoospermic males are exempt from contraceptive requirements. WOCBP who are continuously not heterosexually active are also exempt from contraceptive requirements, and still must undergo pregnancy testing as described in this section.
- g) Women of child-bearing potential who use hormonal contraception must agree to use an additional method of birth control (highly effective or less effective) as detailed in [Appendix 1](#). Female partners of male subjects participating in the study may use hormone based contraceptives as an acceptable method of contraception since they will not be receiving study drug.

Investigators shall counsel WOCBP and male subjects who are sexually active with WOCBP on the importance of pregnancy prevention and the implications of an unexpected pregnancy. Investigators shall advise WOCBP and male subjects who are sexually active with WOCBP on the use of highly effective methods of contraception - (Appendix 1). Highly effective methods of contraception have a failure rate of < 1% when used consistently and correctly.

At a minimum, subjects must agree to use one highly effective method of contraception OR one less effective method as detailed in Appendix 1.

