9 STUDY MANAGEMENT

9.1 Compliance

9.1.1 Compliance with the Protocol and Protocol Revisions

The investigator should not implement any deviation or change to the protocol without prior review and documented approval/favorable opinion of an amendment from the IRB/IEC (and if applicable, also by local health authority) except where necessary to eliminate an immediate hazard(s) to study subjects.

If a deviation or change to a protocol is implemented to eliminate an immediate hazard(s) prior to obtaining relevant approval/favorable opinion(s) the deviation or change will be submitted as soon as possible to:

- IRB/IEC
- Regulatory Authority(ies), if applicable by local regulations per national requirements

Documentation of approval/favorable opinion signed by the chairperson or designee of the IRB(s)/IEC(s) and if applicable, also by local health authority, must be sent to BMS.

If an amendment substantially alters the study design or increases the potential risk to the subject: (1) the consent form must be revised and submitted to the IRB(s)/IEC(s) for review and approval/favorable opinion; (2) the revised form must be used to obtain consent from subjects currently enrolled in the study if they are affected by the amendment; and (3) the new form must be used to obtain consent from new subjects prior to enrollment.

If the revision is done via an administrative letter, investigators must inform their IRB(s)/IEC(s).

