Additional changes include: expansion of time windows for PK sample collection to reduce challenges in collecting samples when subjects are randomized outside of routine working hours; changing requirements for contraception to allow the use of one highly effective method of contraception or one less effective method of contraception to be consistent with BMS SOPs as BMS-986141 is currently considered unlikely to be a teratogen since BMS-986141 produced no developmental toxicity in rats and rabbits when dosed up the maximal feasible dose, 150 mg/kg/day, in expanded range-finding studies; clarified that women enrolled in the study cannot use hormonal contraception as their sole means of contraception; added a statement in Appendix 1 that local laws and regulations may require use of alternative and/or additional contraception methods; added pregnancy test to be done at Day 90 in Part 2; clarified genotyping testing to include the types of genes that will be studied and the location and duration of sample storage; updated protocol to provide further clarifications to assist with study implementation and reflect recent changes in the BMS protocol model document template; corrected typographical errors.

This protocol amendment applies to all subjects to be enrolled in the study.

Changes to the Protocol:

1. Synopsis, Investigational Product(s), Dose and Mode of Administration, Duration of Treatment with Investigational Product(s)
 - a) All treatments: removed approximate number of subjects per treatment arm
 - b) Treatment D: dose changed from 16 mg QD to 8 mg QD
2. Synopsis, Study Design
 - a) Removed the randomization ratio
 - b) Added text stating that initially randomization will be limited to the placebo and the two lower dose treatment groups (0.8 mg QD and 4.8 mg QD), randomization to the highest dose treatment arm (8 mg) will only be initiated after DMC review of safety data from the Day 28 study visit for at least 10% of the planned total subjects.
 - c) Study Schematic:
 - i) Parts 1 and 2 - changed 16.0 mg dose group to 8.0 mg; added note that 8 mg dose group will only be initiated after DMC review of initial safety
 - ii) Part 1 - updated Day 28 to clarify this is end of treatment.

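### Criteria 3d and 3e equate five half-lives with 6 days, but the protocol's stated half-life gives 7.3 to 9.5 days; if that half-life is meant, the 36- and 96-day contraception periods are 1.3 to 3.5 days short

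*Protocol*

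**What the plan says.** Criterion 3d in Protocol Section 3.3.1 sets the post-treatment contraception period for women of childbearing potential as "plus 5 half-lives of study drug BMS-986141 (6 days) plus 30 days (duration of ovulatory cycle) for a total of 36 days post-treatment completion". Criterion 3e builds the period for sexually active men in the same way, "plus 5 half-lives of the study drug (6 days) plus 90 days (duration of sperm turnover"), to a total of 96 days, and applies that period to sperm donation as well. Neither criterion says which half-life is meant or where the 6 days comes from.

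Section 1.4.1.1 reports the pharmacokinetics in healthy subjects: "The mean terminal half-life of BMS-986141 was between 35.2-45.5 hours", and "The accumulation index was < 2 (ranging from 1.3 to 1.9"). Section 1.4.1 describes the repeated dosing in Phase 1 as "multiple doses of up to 30 mg QD for up to 14 days in study CV006003". Other mentions carry no value in hours: Section 1.4.1 gives a relative change of about threefold with itraconazole, and Section 6.4 uses five half-lives for pregnancy reporting without a number. For further pharmacokinetic information, Section 1.4 says that "additional detail can be found in the IB", meaning the Investigator Brochure.

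**The concern.** The criteria state a rule (five half-lives plus one ovulatory cycle or one sperm-turnover period) and then give its value in days. Sites and participants will follow the days, not the rule. If the conversion is wrong, the commitment obtained at enrolment is not the one the protocol set out to obtain, and for men the sperm-donation restriction ends at the wrong time too. Section 6.4 leaves five half-lives unquantified, so a site wanting a number for pregnancy reporting would find only the 6 days in Section 3.3.1.

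**Working it through.** **Inputs.** Six days for five half-lives, with 30 and 90 days added (Section 3.3.1, 3d and 3e). Mean terminal half-life 35.2 to 45.5 h and accumulation index 1.3 to 1.9, stated as below 2 (Section 1.4.1.1). Dosing interval 24 h, from the once-daily Phase 1 dosing in Section 1.4.1.

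**Step 1. The plan's own sums.** 6 + 30 = 36 and 6 + 90 = 96. Both totals follow from the 6-day term, so any error lies in that term.

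**Step 2. Five terminal half-lives.** Days = 5 × t½ / 24.

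| Mean terminal t½ | Five half-lives | Excess over 6 days | Total, women | Total, men |
|---|---|---|---|---|
| 35.2 h | 5 × 35.2 / 24 = 7.33 days | 1.33 days | 37.3 days | 97.3 days |
| 45.5 h | 5 × 45.5 / 24 = 9.48 days | 3.48 days | 39.5 days | 99.5 days |

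Six days (144 h) covers 144 / 45.5 = 3.2 to 144 / 35.2 = 4.1 terminal half-lives, not five.

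**Step 3. The half-life that 6 days implies.** 144 / 5 = 28.8 h. This is below the reported range and is not stated anywhere in the text.

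**Step 4. Does an effective half-life give 6 days?** Under a one-compartment relation, an accumulation index R with 24 h dosing corresponds to t½ = 24 × ln 2 / [−ln(1 − 1/R)].

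| R | Effective t½ | Five half-lives |
|---|---|---|
| 1.3 | 11.3 h | 2.36 days |
| 1.9 | 22.3 h | 4.64 days |
| 2.0 (stated upper bound) | 24.0 h | 5.00 days |

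None gives 6 days. On this reading 6 days is 144 / 22.3 = 6.5 to 144 / 11.3 = 12.7 half-lives, which is more than five, so the periods would not be short.

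**Step 5. Can the amount of drug remaining at 6 days be worked out?** Not safely. If decay followed one exponential, the expected index would be 1 / (1 − 2^(−24/t½)): 2.66 at 35.2 h, 3.27 at 45.5 h and 2.28 at 28.8 h. All exceed the reported 1.3 to 1.9, so elimination is not single-exponential at the terminal rate. A residual percentage based on the terminal half-life would overstate what remains, and none is given here.

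**The case against.** The best reply is that the criteria say half-lives without the word terminal, and the accumulation index suggests that the terminal phase does not drive exposure on once-daily dosing. If the sponsor had an effective half-life in mind, 6 days is generous and participants are fully covered. This stands as far as the shortfall goes: the totals are short only on the terminal reading. It does not explain the 6 days, since the effective half-lives in Step 4 give at most 5.0.

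The effective half-life calculation can itself be questioned. It uses a one-compartment formula for a drug that appears to have more than one phase, and the protocol does not say whether the index refers to peak, trough or area under the curve. An effective half-life of 28.8 h obtained another way therefore cannot be excluded. The Investigator Brochure may also hold a value that supports 6 days, and a few pages of the protocol, including part of the contraception appendix, were not in the text available for this review. If such a value exists, the criteria should cite it; as written, Sections 1.4.1.1 and 3.3.1 do not agree.

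The practical consequence is small. The Amendment 06 rationale says that "BMS-986141 is currently considered unlikely to be a teratogen", and the 30- and 90-day terms make up most of each period.

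**Conclusion.** The concern holds as a minor error. No half-life stated in the available text, and none derived from the accumulation index by the usual one-compartment relation, makes five half-lives equal 6 days. Confidence in that mismatch is high. Confidence that the 36- and 96-day totals are too short, by 1.3 to 3.5 days, is moderate, because it assumes that the terminal half-life is the one intended. That is the natural reading, since it is the only half-life the protocol reports in hours, but the criteria do not say so. This is a wrong or unsupported figure in a safety commitment, not a demonstrated gap in protection. Endpoints, sample size, power and analyses are unaffected.

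**What to change.** In criteria 3d and 3e, replace 6 days with 10 days: five times the upper mean terminal half-life is 9.48 days, rounded up. The totals become 10 + 30 = 40 days for women and 10 + 90 = 100 days for men, including the sperm-donation restriction. Ten days is 240 / 45.5 = 5.3 to 240 / 35.2 = 6.8 terminal half-lives, so the rule is met over the whole reported range of means. Any matching consent text should change with it.

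If the sponsor already holds a half-life that supports 6 days, for example in the Investigator Brochure, it should give the value, type and source in Sections 1.4.1.1 and 3.3.1 and leave the 36 and 96 days as they are. The sponsor should check this first, because it changes nothing for participants.

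The longer periods cost two numbers in each of two criteria, and four more days of contraception for participants and of the sperm-donation restriction for men. Section 9.1.1 does not allow the change "without prior review and documented approval/favorable opinion of an amendment from the IRB/IEC", with health-authority approval where it applies, so it is best carried in an amendment. Neither option affects data collection or the statistical plan.
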